5.2.3. Storage and Handling

Filgotinib tablets should be stored at controlled room temperature of 25 °C (77 °F); excursions are permitted between 15 °C and 30 °C (59 °F to 86 °F). Storage conditions are specified on the label.

Until dispensed to the subjects, all drug products should be stored in a securely locked area, accessible only to authorized site personnel. To ensure the stability of the study drug and to ensure proper product identification, the drug product should not be stored in a container other than the container in which they are supplied. Consideration should be given to handling, preparation, and disposal through measures that minimize drug contact with the body. Appropriate precautions should be followed to avoid direct eye contact or exposure when handling.

5.3. Dosage and Administration of Study Drug

Following completion of Screening and Day -1 assessments, eligible subjects will receive a single oral dose of 100 mg filgotinib (1 × 100 mg tablet) on Day 1, in fasting state. Dosing in subjects with normal hepatic function will begin after a matched subject with hepatic impairment has completed all Day 1 PK assessments.

5.4. Fasting and Meals

Study drug will be administered on Day 1 with 240 mL of water following an overnight fast (no food or drinks except for water) for at least 10 hours. Subjects will continue to fast until after collection of the 4-hour blood sample, relative to study drug dosing. Additionally, subjects will be restricted from water consumption 1 hour before until 2 hours after dosing, except for the 240 mL given with the study treatment. A standardized meal may be provided to subjects after collection of the 4-hour blood draw.

All meals and/or snacks given to subjects during their stay in the clinical study facility will be standardized for all subjects and should be similar in calorie and fat content and taken at approximately the same time each day. All meals provided must be approved by the sponsor. Components of meals (eg, margarine, jelly, bread) should be given to subjects in individual portions (eg, 1 tablespoon) per the approved meal schedule. The provision of meal components in bulk (eg, a jar of jelly for subjects to share) should not be practiced. All meals should be given at approximately the same time each day (eg, 07:30, 12:00, and 18:00).

5.5. Dispensing, Accountability, and Disposal or Return of Study Drug

The investigator (or designee, eg, study center pharmacist) will acknowledge receipt of the study drug (after reviewing the shipment's content and condition) from Gilead (or designee). The investigator will maintain an accurate inventory of all study drug(s). Each dose of the study drug(s) administered at the study center will be administered by qualified study center staff. The dose of study drug(s) administered to subjects in the clinic under the supervision of staff will be

accurately recorded on the Study Drug Accountability form provided by Gilead (or on equivalent documentation maintained by the study center), which indicates the date and quantity of each dosage formulation dispensed to individual subjects.

5.5.1. Study Drug Return or Disposal

Please refer to Section 9.1.7.

5.6. Concomitant Medications and Other Protocol Restrictions

5.6.1. Concomitant Medications

5.6.1.1. Hepatic Impairment Groups

Concomitant use of certain medications or herbal/natural supplements with study drug may result in PK interactions resulting in increases or decreases in exposure of study drug or these medications.

Concomitant medications taken within 30 days of Screening through the FU visit need to be recorded in the source documents and Case Report Form (CRF)/electronic Case Report Forms (eCRFs).

Subjects with hepatic impairment with comorbid diseases not associated with hepatic impairment requiring medication(s) must be taking the medication(s) without a change in dose for at least 2 weeks (or 5 half-lives, whichever is longer) prior to dosing. Any change in the dosage during this timeframe should be reviewed and approved by the Sponsor.

Subjects with hepatic impairment with co-morbid diseases requiring medication(s) must be taking the medication(s) without a change in dose within 28 days of Day 1.

All concomitant medications including over-the-counter and herbal products must be approved by the Investigator and Medical Monitor prior to study enrollment and study drug administration.

The following medications are prohibited from 28 days prior to Day 1 through discharge:

- Any and all illegal or illicit drug use, including use of prescription drugs outside the care of the prescribing physician.
- Hematologic stimulating agents (eg, erythropoiesis-stimulating agents [ESAs]; granulocyte colony stimulating factor [GCSF]; thrombopoietin [TPO] mimetics)
- Chronic systemic immunosuppressants including, but not limited to, corticosteroids azathioprine, or monoclonal antibodies (eg, infliximab).
- Investigational agents or devices for any indication

- Filgotinib is a P-gp substrate. Concomitant use of P-gp inducers or inhibitors with filgotinib may result in changes in exposure of filgotinib or its metabolite GS-829845 and are prohibited from 21 days prior to Day 1 through discharge. Example P-gp inducers and inhibitors are listed below:
 - P-gp inducers: phenobarbital, phenytoin, carbamazepine, rifabutin, rifapentine, rifampin, St. John's wort, and danshen (salvia miltiorrhiza)
 - P-gp inhibitors: amiodarone, azithromycin, captopril, carvedilol, clarithromycin, conivaptan, cyclosporine, diltiazem, dronedarone, erythromycin, felodipine, itraconazole, ketoconazole, lopinavir and ritonavir, quercetin, quinidine, ranolazine, ticagrelor, and verapamil.

Medications for disease conditions **excluded** from the protocol (eg, HIV-1 or HIV-2, HBV, or HCV infection; active cancer; transplantation) are not listed under this Concomitant Medication section and are disallowed in the study.

5.6.1.2. Subjects with Normal Hepatic Function

The following medications are excluded while subjects with normal hepatic function are participating in the study:

- Any prescription medications or over-the-counter medications including herbal products and antacids within 28 days of commencing study drug dosing (Day 1) with the exception of vitamins, acetaminophen, ibuprofen and/or hormonal contraceptives. However, the short term use of topical hydrocortisone cream or non-corticosteroid ointment to treat minor skin irritation due to ECG leads will be allowed. If a subject requires use of a disallowed medication, a request for such use must be reviewed by the Sponsor and if approved, subjects may continue to participate in the study.
- Any and all illegal or illicit drug use, including use of prescription drugs outside the care of the prescribing physician.

5.6.2. Other Protocol Restrictions

- Subjects will be required to refrain from the consumption of food and beverages containing alcohol products 72 hours prior to the first dose of study drug and during the course of the study through the FU visit.
- Subjects will be required to refrain from the use of nicotine or nicotine-containing or THC-containing products 14 days prior to first dose of study drug and during the course of the study through the FU visit.
- Subjects will be required to refrain from consumption of grapefruit juice, grapefruits, and Seville orange juice 72 hours prior to the first dose of study drug and during the course of the study through the FU visit.

- While confined at the study center, tea, coffee, chocolate, and other foods and beverages containing caffeine and other methylxanthines will be prohibited on dosing day. At all other times, caffeine-containing beverages and foodstuffs may be served or withheld in accordance with normal study center practice. Caffeine-containing beverages and foodstuffs will not be restricted while subjects are outside of the clinic.
- Subjects will be encouraged to avoid strenuous or prolonged exercise, as well as saunas, steambaths, and sunbathing or other prolonged ultraviolet exposure, eg, in a tanning salon, from the screening evaluation until completion of the FU visit, as these activities are known to affect certain clinical laboratory test parameters, (eg, creatine kinase) and will provide false indicators of a potentially treatment-related toxicity.

Upon every admission to the clinic, each subject will be questioned as to their compliance with the above protocol restrictions. If a subject is unable to comply with any of the restrictions described above, the subject's continued participation in the study will be reevaluated by the investigator in consultation with the sponsor.

6. STUDY ASSESSMENTS

The study procedures to be conducted for each subject enrolled in the study are detailed below.

Any deviation from protocol procedures should be noted in the subject's clinical chart and appropriate CRFs/eCRFs. In addition, the sponsor should be promptly notified of any protocol deviations.

The study center will not initiate dosing until the following have all been met:

- The institutional review board (IRB)/ethics committee (EC)/other applicable regulatory agencies have reviewed and approved the study and the informed consent document.
- All requested regulatory documents have been submitted to and approved by Gilead.
- A master services agreement and/or study agreement is executed.
- The study initiation meeting has been conducted by the Gilead (or designee).

The initiation meeting will include but is not limited to a review of the protocol, the IB, study drugs, and investigator responsibilities.

Documentation of the personally signed and dated ICF for each subject, using the study-specific, IRB/EC-approved ICF, is required before initiating the screening process.

6.1. Subject Enrollment and Treatment Assignment

Entry into screening does not guarantee enrollment into the study. In order to manage the total trial enrollment, Gilead, at its sole discretion, may suspend screening and/or enrollment at any site or trial-wide at any time.

It is the responsibility of the investigator to ensure that subjects are eligible to participate in the study prior to enrollment and continue to remain eligible throughout the study.

Once the ICF has been obtained, all screening and admission tests and assessments have been assessed, and study eligibility has been confirmed, subjects will be enrolled to receive study drug on Day 1.

Subjects will receive the study treatments as described in Section 5.3.

Table 6-1. Schedule of Assessments

Study Procedure	Screen ^a	Day -1	Day 1	Days 2-5	Day 6 ^b	Day 15 (± 1 day) ^c	ET ^d
Written Informed Consent	X						
Medical History	X						
Complete Physical Exam	X					X	X
Symptom-Driven Physical Examination ^e		X	X	X	X		
Height	X						
Weight, BMI	X	X					
Vital Signs ^f	X	X	X	X ^g	X	X	X
HIV-1/2, HBV, and HCV Testing	X						
Hematology ^h	X	X ⁱ	X		X	X	X
Chemistry ^h	X	X ⁱ	X		X	X	X
Coagulation ^h	X	X ⁱ	X		X	X	X
α-fetoprotein	X						
Urinalysis	X	X ⁱ	X		X	X	X
Serum Pregnancy Test ^j	X	X ⁱ			X	X	X
FSH ^k	X						
Urine Drug, Cotinine, and Alcohol Screen	X	X ⁱ				X	X
12-Lead ECG	X	X	X ^l		X	X	X
Enrollment ^m			X				
Study Drug Administration			X				
PK Assessments ⁿ			X				X
Review Study Restrictions	X	X			X	X	X
Clinic Confinement				X			
Review AEs & Concomitant Medications ^o				X			

a Prospective subjects should be screened no more than 28 days prior to administration of the first dose of study drug.

b Subjects will be discharged from the clinic on Day 6, following all morning assessments.

c Subjects will return for a FU visit on Day 15 (± 1 day).

- d Assessments will be performed within 72 hours of early termination (ET) from the study.
- e Symptom-driven PEs will be performed during confinement as needed, based on reported signs and symptoms.
- f Vital signs include blood pressure, heart rate, respiration rate, and body temperature.
- g Day 3 only.
- h Hematology, Chemistry, Coagulation: See Section 6.9.5.1 for specifics.
- i Two sets of safety labs will be collected upon clinic admission; one will be sent to the central lab and another will be sent to the sites' local lab to obtain results in time for enrollment on Day 1.
- j Females of child-bearing potential only.
- k Female subjects < 54 years old with amenorrhea \geq 12 months as outlined in Appendix 3
- l 2 hours postdose.
- m On Day 1, subjects will be enrolled immediately prior to dosing.
- n Intensive PK sampling will occur relative to dosing of filgotinib on Day 1 at the following time points for each cohort: Day 1: 0 (predose, \leq 5 min before dose), 0.5, 1, 2, 3, 4, 5, 6, 8, 12, 18, 24, 36, 48, 72, 96, and 120 hours postdose. A blood sample for PK analysis will be collected at the ET visit (if applicable) and may be analyzed.
- o From the time of obtaining informed consent through the first administration of study drug, record all SAEs, as well as any nonserious AEs related to protocol-mandated procedures on the AE eCRF. All other untoward medical occurrences observed during the screening period, including exacerbation or changes in medical history, are to be captured on the medical history eCRF. See Section 7, Adverse Events and Toxicity Management for additional details.

6.2. Pretreatment Assessments

6.2.1. Screening Visit

Prospective subjects should be screened no more than 28 days prior to administration of the first dose of study drug. If a subject does not begin the treatment phase within this 28-day window, all screening evaluation procedures must be repeated. Screening laboratory assessments may be repeated once within 28 days prior to administration of study drug to rule out laboratory error.

A sufficient number of subjects will be screened to identify up to 60 subjects for enrollment.

Subjects should be instructed to fast (no food or drink, except water), starting from midnight (00:00) or earlier, as appropriate, on the evening prior to the screening visit to ensure an approximate 8-hour fast prior to the fasted blood sample collection the next morning.

Written informed consent must be obtained from each subject before initiation of any screening procedure. After a subject has provided informed consent, the investigator and other study personnel will determine if the subject is eligible for participation in the study. This assessment will include a review of the inclusion/exclusion criteria and completion of all screening procedures as outlined in [Table 6-1](#) and described in the following text.

Eligible subjects meeting all of the inclusion criteria and none of the exclusion criteria will be instructed on all protocol requirements, including the restrictions on concomitant medication usage and other substances as well as consumption of food or beverages containing alcohol, caffeine, or xanthine. Subjects will be asked to arrive at the study center on Day -1 for admission assessments.

From the time of obtaining informed consent through the first administration of study drug, record all SAEs, as well as any AE related to protocol-mandated procedures on the AE CRF/eCRF. All other untoward medical occurrences observed during the screening period, including exacerbation or changes in medical history are to be captured on the medical history CRF/eCRF. See Section 7 Adverse Events and Toxicity Management for additional details.

6.2.2. Admission Assessments

6.2.2.1. Admission

Subjects should be instructed to fast (no food or drink, except water), starting from midnight (00:00) or earlier, as appropriate, on the evening prior to the screening visit to ensure an approximate 8-hour fast prior to the fasted blood sample collection.

Subjects meeting all eligibility criteria following the screening evaluation will return to the clinic for admission assessments on Day -1. The admission evaluations and/or procedures are outlined in [Table 6-1](#).

Prior to dosing on Day 1, the results of the clinical and laboratory evaluations (as described in [Table 6-1](#)) must be reviewed by the investigator to confirm the continued eligibility of each subject to participate in the study. At the time of enrollment, subjects will be assigned a sequential subject number as described in Section 5.1. Subjects will remain confined to the study clinic for the duration as described in Section 6.2.2.2 and [Table 6-1](#).

6.2.2.2. Clinic Confinement

Following Screening and admission assessments, eligible subjects will be confined to the study center beginning Day -1 until the completion of assessments on Day 6. Subjects will return for an in-clinic FU visit on Day 15 (± 1 day).

6.3. Check-in Assessments

Following completion of screening and Day -1 assessments, eligible subjects will be assigned a subject number and receive study treatments as shown in Section 5.3.

6.4. Treatment Assessments

Study procedures and assessments are outlined in [Table 6-1](#).

6.5. Posttreatment Assessments

Subjects will return for an in-clinic FU visit on Day 15 (± 1 day). Study procedures and assessments are outlined in [Table 6-1](#).

6.6. Assessments for Premature Discontinuation from Study

If the subject withdraws from the study, the ET evaluations and/or procedures outlined in [Table 6-1](#) should be performed within 72 hours of permanently discontinuing the study drug.

6.7. Study Stopping Criteria

If ≥ 2 subjects in any cohort experience the same or similar Grade 3 or Grade 4 treatment-emergent AE or confirmed laboratory abnormality that is not attributable to obvious alternative explanation (eg, hematuria occurring in a menstruating female, creatine kinase [CK] elevation after strenuous exercise, or triglyceride elevation that is non-fasting, etc), a review of all safety data generated in subjects dosed to date will be initiated. The decision as to whether and how to proceed with further enrollment will be determined based on the safety review.

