Vital Signs (blood pressure, pulse, respiration rate, and temperature): Screening, Days -1, 1, 3, 6, and the FU or the ET visit (if applicable)

Height: Screening

Weight: Screening and Day -1

Clinical Laboratory Tests (hematology, blood chemistry including coagulation, and urinalysis): Screening, Days -1, 1, 6, and the FU or the ET visit (if applicable)

Urine Drug, Cotinine, and Alcohol Assessments: Screening, Day -1 and the FU or the ET visit (if applicable)

12-lead electrocardiogram (ECG): Screening, Days -1, 1 (2 hours post dose), 6, and the FU or ET visit (if applicable)

Serum Pregnancy Test (women of childbearing potential only): Screening, Days -1, 6 and the FU or the ET visit (if applicable)

Serology Test (HBV, HCV, HIV): Screening

α -fetoprotein Test: Screening

Assessment of adverse events (AE) and concomitant medications will continue throughout the study. All clinical AEs and clinically significant laboratory abnormalities will be managed according to uniform guidelines detailed in protocol [Appendix 3](#)

Protocol-Specific Stopping Rules

If ≥ 2 subjects in any cohort experience the same or similar Grade 3 or Grade 4 treatment-emergent AE or confirmed laboratory abnormality that is not attributable to obvious alternative explanation (hematuria occurring in a menstruating female, creatine kinase [CK] elevation after strenuous exercise, or triglyceride elevation that is non-fasting, etc), a review of all safety data generated in subjects dosed to date will be initiated. The decision as to whether and how to proceed with further enrollment will be determined based on the safety review.

Test Product, Dose, and Mode of Administration:

A single dose of 100 mg filgotinib (1 x 100 mg tablet), in a fasted state.

Reference Therapy, Dose, and Mode of Administration:

Not applicable

Criteria for Evaluation:

Safety: Safety will be assessed during the study through the reporting of AEs, and by clinical laboratory tests, physical examinations, vital signs, and ECGs at various time points during the study.

Efficacy: Not applicable.

Pharmacokinetics: The following plasma PK parameters of filgotinib and its metabolite (GS-829845) will be calculated, as appropriate: C_{max} , T_{max} , C_{last} , T_{last} , λ_z , AUC_{last} , AUC_{inf} , $\%AUC_{exp}$, $t_{1/2}$, CL/F , and V_z/F .

Statistical Methods:**Pharmacokinetics:**

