7.2.2. Assessment of Severity

The severity of AEs will be graded using the modified Common Terminology Criteria for Adverse Events (CTCAE) version 4.03. For each episode, the highest grade attained should be reported.

If a CTCAE criterion does not exist, the investigator should use the grade or adjectives: Grade 1 (mild), Grade 2 (moderate), Grade 3 (severe), Grade 4 (life-threatening) or Grade 5 (fatal) to describe the maximum intensity of the adverse event. For purposes of consistency with the modified CTCAE, these intensity grades are defined in [Table 7-1](#) and [Appendix 4](#).

Table 7-1. Grading of Adverse Event Severity

Grade	Adjective	Description
Grade 1	Mild	Asymptomatic or mild symptoms; clinical or diagnostic observations only; intervention not indicated
Grade 2	Moderate	Local or noninvasive intervention indicated; limiting age-appropriate instrumental ADL*
Grade 3	Severe	Severe or medically significant but not immediately life-threatening; hospitalization or prolongation of hospitalization indicated; disabling; limiting self-care ADL**
Grade 4	Life-threatening	Urgent intervention indicated
Grade 5	Death	Death related AE

* Activities of Daily Living (ADL) Instrumental ADL refer to opening preparing meals, shopping for groceries or clothes, using the telephone, managing money, etc.

** Self-care ADL refer to bathing, dressing and undressing, feeding self, using the toilet, taking medications, and not bedridden.

7.3. Investigator Requirements and Instructions for Reporting Adverse Events and Serious Adverse Events to Gilead

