7.5. Clinical Laboratory Abnormalities

Laboratory abnormalities are usually not recorded as AEs or SAEs. However, laboratory abnormalities (eg, clinical chemistry, hematology, and urinalysis) independent of the underlying medical condition that require medical or surgical intervention or lead to interventional medicinal product interruption or discontinuation must be recorded as an AE, as well as an SAE, if applicable. In addition, laboratory or other abnormal assessments (eg, ECG, X-rays, vital signs) that are associated with signs and/or symptoms must be recorded as an AE or SAE if they meet the definition of an AE (or SAE) as described in Sections 7.1.1 and 7.1.2. If the laboratory abnormality is part of a syndrome, record the syndrome or diagnosis (eg, anemia) not the laboratory result (eg, decreased hemoglobin).

Adverse events will be coded using the most recent version of the Medical Dictionary for Regulatory Activities (MedDRA). Severity should be recorded and graded according to the modified CTCAE, version 4.03 ([Appendix 4](#)).

For AEs associated with laboratory abnormalities, the event should be graded on the basis of the clinical severity in the context of the underlying conditions; this may or may not be in agreement with the grading of the laboratory abnormality.

All clinical and clinically significant laboratory toxicities will be managed according to uniform guidelines detailed in [Appendix 3](#).

For study specific stopping criteria, please refer to Section [6.7](#).

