7.6. Toxicity Management

Treatment-emergent toxicities will be noted by the investigator and brought to the attention of the Gilead medical monitor, who will have a discussion with the investigator and decide the appropriate course of action. Whether or not considered treatment-related, all subjects experiencing AEs must be monitored periodically, when feasible, until symptoms subside, any abnormal laboratory values have resolved or returned to baseline levels or they are considered irreversible, or until there is a satisfactory explanation for the changes observed.

Grade 3 and 4 clinically significant laboratory abnormalities should be confirmed by repeat testing as soon as practical to do so, and preferably within 3 calendar days after receipt of the original test results and followed until resolution or until stable, if possible. Refer to [Appendix 2](#) for additional details on toxicity management.

Any questions regarding toxicity management should be directed to the Gilead medical monitor.

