#### **7.1.2. Adverse Event Severity**

Adverse events are graded by the investigator as Grade 1, 2, 3, 4, or 5 according to toxicity criteria specified in the protocol. The severity grade of events for which the investigator did not record severity will be categorized as “missing” for tabular summaries and data listings. The missing category will be presented last in the summary presentation.

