## **7.1.7. Summaries of Adverse Events and Deaths**

Treatment-emergent AEs will be summarized based on the Safety Analysis Set.

The number and percentage of subjects who experienced at least 1 TEAE will be provided and summarized by SOC, PT, and hepatic function group based on the Safety Analysis Set as follows:

- All TEAEs
- All TEAEs by SOC and PT
- All TEAEs by severity

- All treatment-related AEs
- All TEAEs of Grade 2 or higher
- All treatment-related AEs by severity
- All treatment-emergent SAEs
- All TEAEs leading to study discontinuation

A brief, high-level summary of AEs described above will be provided by hepatic function group and by the number and percentage of subjects who experienced the above AEs. All deaths observed in the study will also be included in this summary.

Multiple events will be counted only once per subject in each summary. Adverse events will be summarized and listed first in alphabetic order of SOC and then by PT in descending order of total frequency within each SOC. For summaries by severity, the most severe grade will be used for those AEs that occurred more than once in an individual subject per treatment during the study.

In addition, data listings will be provided for the following:

- All AEs (indicating whether the event is treatment emergent)
- All SAEs
- Deaths

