#### 7.2.2.2. Summaries of Laboratory Abnormalities

Laboratory data that are categorical will be summarized using the number and percentage of subjects in the study with the given response at predose and each scheduled postdose time point.

The following summaries (number and percentage of subjects) for treatment-emergent laboratory abnormalities will be provided by laboratory test and hepatic function group; subjects will be categorized according to the most severe postdose abnormality grade for a given laboratory test:

- Treatment-emergent Graded laboratory abnormalities
- Treatment-emergent Grade 3 or higher laboratory abnormalities

For all summaries of laboratory abnormalities, the denominator is the number of subjects with nonmissing postdose values up to 30 days after last dosing date.

A by-subject listing of treatment-emergent laboratory abnormalities will be provided by subject ID number and time point in chronological order. This listing will include all test results that were collected throughout the study for the lab test of interest, with all applicable severity grades displayed.

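### The two-subject safety-review trigger names only Grades 3 and 4, so a fatal (Grade 5) event with no earlier Grade 3 or 4 phase does not count toward it

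*Protocol*

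**What the plan says.** Protocol section 6.7 sets the study's stopping criteria. The trigger is at least two subjects in any cohort who "experience the same or similar Grade 3 or Grade 4 treatment-emergent AE or confirmed laboratory abnormality", unless there is an obvious alternative explanation. Once met, all safety data from subjects dosed so far are reviewed, and that review decides whether and how enrollment continues. The synopsis repeats the rule with the same two grades: "Grade 3 or Grade 4 treatment-emergent AE or confirmed laboratory abnormality that is not attributable to obvious alternative explanation (hematuria occurring". Protocol section 7.5 directs readers to 6.7 as the place for study-specific stopping criteria ("For study specific stopping criteria, please refer to Section").

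The severity scale has five levels. Protocol section 7.2.2 lists "Grade 4 (life-threatening) or Grade 5 (fatal") as separate grades, Table 7-1 repeats them, and the highest grade reached in an episode is the one reported. SAP section 7.1.2 agrees: "Adverse events are graded by the investigator as Grade 1, 2, 3, 4, or 5".

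Elsewhere the SAP uses open-ended grade categories: "All TEAEs of Grade 2 or higher" in section 7.1.7 and "Treatment-emergent Grade 3 or higher laboratory abnormalities" in section 7.2.2.2.

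**The concern.** A trigger based on severity should not become less sensitive as severity rises. By naming two grades and stopping there, section 6.7 leaves out the worst outcome on the protocol's own scale. A death that passed through a Grade 3 or 4 phase arguably counts, because the rule turns on what a subject experiences. A death without such a phase does not count.

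At stake is whether a full safety review and an enrollment decision are required or left to discretion when a cohort has a direct death together with a similar severe event. The trigger does not itself halt dosing. No endpoint, sample size or pharmacokinetic analysis is affected.

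**Working it through.** The plan states no operating characteristic for this rule, so there is no figure to reproduce. The check applies the rule to the possible cases.

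**Inputs**
- Threshold: at least 2 subjects in one cohort (Protocol 6.7).
- Grades counted now: 3 and 4 (Protocol 6.7 and synopsis).
- Scale: 1 to 5, with 5 fatal (Protocol 7.2.2 and Table 7-1; SAP 7.1.2).
- Recording: highest grade per episode (Protocol 7.2.2).

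**Rule.** Let N be the number of subjects in a cohort whose similar, otherwise unexplained events carry a counted grade. The review starts if N ≥ 2. The current wording counts {3, 4}; the amended wording counts {3, 4, 5}.

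**Reading A: what the subject experienced.** Let P be a subject with a Grade 3 or 4 phase, whether or not the event is later fatal. Let D be a subject with a fatal event and no such phase.

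| Subjects | N now | Review now | N amended | Review amended |
|---|---|---|---|---|
| P + P | 1 + 1 = 2 | yes | 2 | yes |
| P + D | 1 + 0 = 1 | no | 2 | yes |
| D + D | 0 + 0 = 0 | no | 2 | yes |
| D alone | 0 | no | 1 | no |

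**Reading B: the grade recorded for the episode.** Any death is recorded as Grade 5, even after a Grade 3 or 4 phase.

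| Recorded grades | N now | Review now | N amended | Review amended |
|---|---|---|---|---|
| 4, 4 | 2 | yes | 2 | yes |
| 4, 3 | 2 | yes | 2 | yes |
| 5, 3 | 1 | no | 2 | yes |
| 5, 4 | 1 | no | 2 | yes |
| 5, 5 | 0 | no | 2 | yes |

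Reading A is the narrower of the two and is the one the conclusion rests on. Reading B would widen the gap. The rows are cases, not probabilities.

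**Do other provisions close the gap?**
- Protocol 7.6: toxicities go to the medical monitor, "who will have a discussion with the investigator and decide the appropriate course of action". There is no two-subject threshold, but no full review is required.
- Protocol 7.3.1.3: serious events are transmitted within 24 hours, with hospital and autopsy reports on fatal events when requested. This is reporting only.
- Protocol 7.4: applicable SUSARs are notified to regulators, ethics committees and investigators. This is notification only.
- Protocol 9.1.6: the sponsor monitors safety data centrally. No trigger is set.
- Protocol 6.1 and 9.3.4: enrollment may be suspended or the study terminated. Both are discretionary.
- Protocol 1.3 and 8.5: Cohort 1 data are reviewed before the adaptive cohorts are dosed. This does not cover events arising later within an adaptive cohort.
- SAP 2.1: there is no data monitoring committee.

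None of these makes a Grade 5 event count toward 6.7 or requires the review that 6.7 requires.

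**The case against.** The strongest reply is that the affected case is close to empty. Given how Table 7-1 defines Grades 3 and 4, few deaths would skip both. Such a death must also be paired with a similar event in the same cohort, with no obvious other explanation, after one 100 mg dose of a drug the protocol describes as well tolerated in 1462 subjects (section 1.4). A death would reach the sponsor quickly by routes with no two-subject threshold, and nobody is likely to have meant to exclude deaths. The proposed wording still does nothing for a single death. The SAP's open-ended grades are table categories, not safety triggers. On this view the point is an editorial note.

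Much of this stands. The event is improbable, inaction after a death is unlikely, and the SAP comparison shows only that open-ended wording was available. Appendix 2, to which section 7.6 refers for toxicity management, appears only as a heading in the available text. A fatal-event instruction there cannot be excluded, although 6.7 does not cite that appendix.

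The reply does not make the rule correct. If the drafters meant deaths to count, the words should say so. Once an adaptive cohort is enrolling, 6.7 is the only prespecified event-count trigger for a full safety review in the available text. Cohort 2 would take subjects with CPT scores of 10 to 15, and the laboratory criteria allow platelets down to 25,000/mm³ and INR up to 2.3 (Protocol 4.2.2).

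**Conclusion.** The concern holds as a minor wording correction that should be made. Followed literally, section 6.7 requires a full safety review for two similar Grade 3 events but not for two direct deaths, or for a direct death plus a similar Grade 3 or 4 event. The gap is narrow and of low probability. The documents give no fatal-event rate, so it cannot be quantified further.

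The conclusion assumes that a death preceded by a Grade 3 or 4 phase does count, which is the reading more favorable to the plan. It also assumes that the unseen body of Appendix 2 contains no instruction that brings Grade 5 events under 6.7.

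**What to change.** At the next amendment, change the two named grades to *Grade 3 or higher* in Protocol section 6.7 and in the synopsis stopping rule. Keep the two-subject condition. If the sponsor also wants one death to start the review, add *or any Grade 5 event*; that is a separate choice.

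The cost is one phrase in two places. The amendment needs IRB/EC submission and documented approval (Protocol 9.1.2 and 9.2.1) for centers in three countries. It adds no procedures, visits or samples.
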